[H2a] Perceived CVD and diabetes risks, perceived life expectancies and subjective survival probabilities are correlated with objective risks predicted from risk factors, including demographics, BMI etc.

Test:

- Regress perceived personal risks from both information treatment group and control group on 10year CVD risk predicted from Globorisk, 10-year diabetes risk predicted from Finnish Diabetes Risk Score (FINDRISC) (Lindstrom and Tuomilehto 2003) and lifetable survival probabilities.³
- Data from section D prior to treatment group receiving information on personal CVD risk.

[H2b] Perceived CVD and diabetes risks, and perceived life expectancies, deviate from predicted risks due to differential weighting of risk factors.

Test:

- Regress perceived personal risks of both information treatment group and control group (section D) on risk factors and compare coefficients with those obtained from regression of predicted probabilities on risk factors. For example, for personal 10-year CVD risk, compare coefficients from model of reported probability to those used in Globorisk risk prediction tool to produce predicted probabilities. Moreover, compare other coefficients to those found in previous literature on the determinants of CVD and diabetes risks, and on life expectancies, such as, family history and exercise.
- Regress perceived personal CVD and diabetes risks, life expectancies and subjective survival probabilities (section D) on the respective perceived base rates (section B) and on risk factors to test the extent to which perceived personal risks are based on perceived base rates with an adjustment to make use of information available to the respondent on risk factors.

[H2c] Perceived base rates for CVD, diabetes, life expectancy and survival probability are higher than objective (predicted) base rates.

Tests:

- Compute mean deviations of perceived base rates (section B) from predicted base rates. A positive (negative) mean deviation hints at overestimation (underestimation) of CVD prevalence/diabetes prevalence/life expectancy/survival probability.
- Compute mean ratios of perceived base rates to objective (predicted) base rates. A mean ratio > 1 (< 1) hints at overestimation (underestimation) of CVD prevalence/diabetes prevalence/life expectancy/survival probability.
- Compare proportion of sample with perceived base rate < objective (predicted) base rate with proportion with perceived base rate > objective base rate.

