³ This test could be conducted using all survey respondents, including those in the lottery intervention arm. The reason we exclude the latter is because later tests make use of the information intervention and we want to have a consistent sample throughout.

[H2d] The accuracy of base rate estimates varies with education, personal risks, life expectancies and survival probabilities, the respondent's confidence in the accuracy of his perceived base rate, the respondent's degree of worry about CVDs, the respondent's degree of dispositional optimism, and possibly other characteristics.

Tests:

- Repeat computation of mean deviations and mean ratios as explained in [H2c] for each gender/age category combination and check whether CVD/diabetes prevalence, life expectancy and survival probabilities are systematically (by factors defined in [H2d]) over- or underestimated.
- Regress mean square estimation error ((perceived predicted)²) and binary indicator of whether base rate has been over- or underestimated on education level, predicted personal CVD/diabetes risk, predicted life expectancies and survival probabilities, confidence about own base rate estimates, worry about CVDs, dispositional optimism, and possibly other characteristics.

[H2e] Perceived personal CVD risk is negatively correlated with perceived life expectancies and survival probabilities.

- Regress perceived personal CVD risk on perceived life expectancies and on survival probabilities until the age of 80 years (section D).
- Compute fraction of respondents who state a perceived life expectancy conditional on experiencing a CVD event lower than their unconditional perceived life expectancy.

[H2f] Perceived personal CVD and diabetes risks, life expectancies and subjective survival probabilities deviate systematically from base rates with a tendency towards optimism bias.

Tests:

- Compute mean deviations of prior perceived personal risk (section D) from predicted base rate for treatment and control group. A negative mean deviation is consistent with optimism bias.
- Compare the mean deviation of the treatment group that is given information on the base rate (section C) with the control group that is not. Establish the extent to which under-/over-estimation of the base rate contributes to apparent optimism/pessimism bias.
- Compute mean ratio of perceived personal risk to predicted base rate for treatment and control group. A mean ratio < 1 is consistent with optimism bias.

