To mitigate concerns that our respondents might be unfamiliar with the formal concept of probability, we will ask them to mark a number of coloured dots from 100 arranged in a square on a tablet screen (Figure 1). The respondent is asked a question, such as: "What do you think is the chance that you will have a heart attack or a stroke within the next 10 years?" The interviewer shows the respondent the square of dots and instructs her to mark the number that she thinks corresponds to that chance. When marked, the dots change colour. The respondent's reported probability, i.e. the number of marked dots, is also visible to the respondent as a number next to the figure. A similar approach has been used by Kerwin (2016), who uses a diagram of 100 pairs of stick figures representing couples, to elicit perceptions of the HIV transmission rate.

35

Figure 1 Belief elicitation tool

A potential concern when asking expectations questions is the tendency for probabilities to heap at the "focal" probability of 50%. This response may reflect the respondent's uncertainty about the probability rather than a precise evaluation that there is a 50:50 chance of the event occurring (Delavande and Kohler, 2009). In training questions, we follow the Health and Retirement Study and Kerwin (2016) by asking respondents who report 50% whether they really believe that the probability is 50%, or whether they are just not sure. This forces the respondent to consider what a response of 50% really means, and it gives us the option to control for respondents who have a tendency to give a focal response when they are not sure.

The risk perceptions module consists of eight sections. The first section familiarizes the respondent with probabilities and use of the belief elicitation tool. It starts with a simple explanation of probabilities using the example of the chance of a destructive earthquake within the following 12 months. The respondent then has to answer a number of expectations questions related to the example. The answers are used to test whether the elicited beliefs are consistent with basic properties of probabilities, such as monotonicity.

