Section 2 asks the respondent to report the chance that someone of the same age and gender will have a heart attack or a stroke within ten years. This is interpreted as the respondent's perception of the CVD base rate. Section 3, as well as Sections 5-7, is completed only by respondents in the information treatment group. These sections are described in the next section of this document. In section 4, the respondent is asked to report the chance that she will have a heart attack or a stroke in the next ten years. This is interpreted as the prior belief of personal CVD risk. In Section 8, the respondent is asked to report what her chance of a heart attack or stroke within ten years would be if she were to adopt healthier behaviour, i.e. to quit smoking (if a smoker) and to control blood pressure and weight.

After stating her perceived CVD risk in Sections 2 and 4 (and 6), the respondent is asked how confident she is in her answer on a five-point scale ranging from 1 (not at all confident) to 5 (extremely confident).

Respondents are likely to differ in how certain they are that the stated probability is close to the actual probability of having a heart attack or a stroke. Moreover, in Section 4 (and 6) the participant is asked how worried she is about having a heart attack or a stroke on a five-point scale ranging from 1 (not at all worried) to 5 (extremely worried).

5. Interventions

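### H2c and H2f set no rule for 50% answers that mean 'not sure', so the CVD mean deviation and mean ratio can be pushed upward without any true overestimation

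*Combined protocol and SAP*

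**What the plan says.** Section 4 (Elicitation of risk perceptions) discusses heaping at 50% and says of such an answer: "This response may reflect the respondent's uncertainty about the probability rather than a precise evaluation that there is a 50:50 chance of the event occurring". It then places the remedy: "In training questions, we follow the Health and Retirement Study" and one other study, by "asking respondents who report 50% whether they really believe that the probability is 50%, or whether they are just not sure". The stated use is permissive: "it gives us the option to control for respondents who have a tendency to give a focal response when they are not sure".

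The same section describes the CVD questions. After the perceived CVD risks in sections 2 and 4 (B and D in Table 1), and again in section 6 (F), "the respondent is asked how confident she is in her answer on a five-point scale". Sections 4 and 6 add a worry item. No 50% follow-up is described for any of them.

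In section 3.2, H2c predicts that perceived base rates are too high. It uses three summaries of the section B answers: mean deviation, mean ratio, and the shares below and above the predicted rate. The first is read as follows: "A positive (negative) mean deviation hints at overestimation (underestimation) of CVD prevalence/diabetes prevalence/life expectancy/survival probability". H2f applies the same kinds of summary to section D answers, with the rule "A negative mean deviation is consistent with optimism bias". Neither hypothesis mentions 50% answers, the training-question flag, or a sensitivity analysis for them.

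**The concern.** The plan identifies a measurement problem and does not carry the remedy into the tests most exposed to it. The predicted CVD rate is far below 50%, so an answer of 50 given for want of a view is always a large positive error, and an answer near zero can offset it by no more than about 11 points. In H2c the error runs in the direction of the hypothesis. In H2f it runs against the optimism the plan expects and can cancel it.

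Accuracy of beliefs is part of the project's first objective (section 3.1), so these readings matter. If 'not sure' is recorded only on the earthquake items, no later analysis can identify someone who first answers 50 for that reason on a CVD item. Leaving the control optional also means that the choice could be made after the results are seen.

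**Working it through.** **Inputs from the documents.** Mean 10-year CVD risk 11.35% (section 10.1), used here as one common base rate. Control 1,361 and information 299 (Table 6, binary-outcome column), together 1,660; the lottery arm is left out of the belief tests (footnote 3). ICC 0.1 and 10 per cluster give a design effect of 1 + 9 × 0.1 = 1.9. Significance level 5%, taken as two-sided.

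**Assumptions not in the documents.** Share s of uninformative 50s: 5% or 10%. SD of the other perceived risks: 10 to 30 points. Belief ICC equal to 0.1.

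**1. The plan's own figure.** The plan gives no figure for the belief tests. Its sample-size inputs do reproduce: 2 × (1.960 + 0.842)² / (0.2 × 0.6)² ≈ 1,091 per arm; × (1 − 0.6²) × 1.9 ≈ 1,327, against 1,306 in Table 6 for mean CVD risk (within 2%).

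**2. H2c mean deviation and ratio.** Suppose everyone else is right on average.
- Shift = s × (50 − 11.35) = 38.65s: +1.93 points at 5%, +3.87 at 10%.
- Ratio = 1 + s × (50/11.35 − 1): 1.17 at 5%, 1.34 at 10%.
- SE = √{[(1 − s)SD² + s(1 − s)38.65²] × 1.9/1,660}.

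| Share s | z, SD 10 | z, SD 20 | z, SD 30 |
|---|---|---|---|
| 5% | 4.4 | 2.7 | 1.9 |
| 10% | 7.6 | 5.1 | 3.7 |

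The smallest share reaching z = 1.96 is 2.0%, 3.6% and 5.25% respectively.

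**3. H2c above/below comparison.** With the rest split evenly, the share above is 0.5 + s/2, and z = (s/2)/√(0.25 × 1.9/1,660).
- 5%: 52.5% above, z = 1.48.
- 10%: 55% above, z = 2.96.
- Share needed for 1.96: about 6.6%. Using the baseline number before attrition, 1,660/0.9 = 1,844, it is about 6.3%.

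**4. H2f mean deviation.** True optimism of d points appears as −(1 − s)d + 38.65s, which is zero at d = 38.65s/(1 − s).
- 5%: d = 2.03 points (18% of 11.35).
- 10%: d = 4.29 points (38% of 11.35).
- Control arm, SD 20, s = 10%: a true −4 (z = −5.4 without the 50s) appears as +0.27 (z = 0.3); a true −6 appears as −1.54 (z = −1.8).

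**5. H2f proportion test at s = 10%.** The share below becomes 0.9 × the true share, and z = (share − 0.5)/√(0.25 × 1.9/n).

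| True split | Observed below | z, control (1,361) | z, information (299) |
|---|---|---|---|
| 55:45 | 49.5% | −0.3 | −0.1 |
| 60:40 | 54.0% | 2.1 | 1.0 |
| 65:35 | 58.5% | 4.6 | 2.1 |

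**6. If the unsure do hold a higher belief.** If their real belief is 30%, each 50 adds 20 points, not 38.65. The distortion is then 1.0 point at 5% and 2.0 points at 10%.

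**The case against.** The plan is not without tools. It has the training flag, and it records confidence on the same B, D and F answers. H2d regresses the size and direction of base-rate error on confidence, and H3c lets the updating weight vary with it. This stands, and it rules out the reading that uncertainty is ignored. But H2c and H2f themselves use neither measure, and low confidence alone does not separate a considered 50 from a 'not sure' 50.

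H2f also does not rest on the mean alone. Its proportion test is chosen as less sensitive to outliers. The control-arm comparison of D with B gives zero for someone who answers 50 to both. A survival-to-80 check might reveal a general pull towards 50, although the plan's reading of the sign there needs reconciling with the event's positive valence. These checks limit the damage but do not correct the mean and ratio.

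Stronger readings that a reader might infer are not supported:
- That 5% is enough to establish overestimation. It falls short on the above/below comparison and, at SD 30, on the mean. The plan also says only that the deviation hints at it.
- That 10% hides optimism generally. In the control arm a 60:40 split remains visible.
- That all H2c quantities are affected. Life expectancy is in years. Effects on diabetes and survival depend on base rates that the plan does not give.
- That the same share drives H3d. Its prior is elicited after the respondent has been told the base rate (section 5.2), so a share assumed for uninformed answers cannot be carried over.

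Finally, the questionnaire (Appendix C) was not available, so the placement of the follow-up rests on section 4's description.

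**Conclusion.** The gap is real but limited. As written, the CVD mean deviation and mean ratio in H2c and H2f take every 50 at face value. With shares of 5% to 10%, the H2c mean is overstated by 1.9 to 3.9 points if the unsure would otherwise average 11.35%, or by 1.0 to 2.0 points if their real belief is about 30%. At 10%, mean optimism of about 4.3 points would disappear under the first of these assumptions. The above/below comparisons are more robust but not immune: about 6% to 7% suffices in H2c, and a 55:45 optimistic split is lost in H2f at 10%.

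The share, the belief SD, the common base rate and the belief ICC are all assumptions. The trial's principal outcome, Globorisk-predicted risk, is not affected.

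**What to change.** Ask the existing follow-up question whenever 50 is marked in sections B, D and F. Pre-specify that the H2c and H2f CVD results are reported twice, with all answers and without the 'not sure' 50s, together with the number of such answers. Conclude overestimation, or absence of optimism, only if it holds in both.

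If the questionnaire cannot change, run the same paired analysis using the training-question flag together with low confidence on the same item, with the cut on the five-point scale fixed in advance. For regression (3.1) and H3d, use exclusion only as a sensitivity analysis: dropping unsure respondents selects on confidence, which H3c is meant to study.

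The cost is one short item for those who mark 50, a few seconds of interview time, and a few lines in the analysis plan. One of the two analyses will omit the least certain respondents, which is why both should be shown.

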3.2 Hypotheses and tests

We first propose hypotheses regarding relationships between CVD beliefs, information and behaviour that will be tested using data on elicited beliefs and the information experiment, which are summarized in Table 1.

Q1: Are the elicited beliefs interpretable as subjective probabilities?

[H1a] Elicited probabilities have face validity and are consistent with rules of probability.

Tests:

- Use data from section A.
- Face validity: Ask for perceived life expectancy and for perceived chance of living past 80 years. Check whether those variables are positively correlated.
- Monotonicity: Ask for perceived probability of a destructive earthquake in respondent's province within one year and within 10 years and check percentage of respondents for whom the latter reported probability is not smaller than the former.
- Binary complementarity: Ask for perceived probability that there will be a destructive earthquake in respondents' province within the next 10 years and perceived probability that there will NOT be a destructive earthquake during the same period. Check percentage of respondents for whom the probabilities add up to 1. Compute mean sum of those two subjective probabilities and test whether it equals 1.

[H1b] The prevalence of consistency violations varies with education.

Test:

• Regress binary outcome indicating violation of probability rule (monotonicity and binary complementarity) on education level (and possibly other characteristics).

1 au	ie i Overview of fisk perceptions survey module				
Sect	ion	Treatment group	p Control group		
A.	Training questions	A_{T}	A _C		
B.	Perceived average CVD risk (base rate)	B_{T}	B_{C}		
C.	Information on average CVD risk	C_{T}			
D.	Perceived personal CVD risk (prior)	D_{T}	D_{C}		
E.	Information on personal CVD risk	E _T			
F.	Perceived personal CVD risk (posterior)	F _T			
G.	Information on CVD risk if reduce risk factor exposure	G _T			
Н.	Perceived personal CVD risk if reduce risk factor exposure	H_{T}	H_{C}		

Table 1 Overview of risk perceptions survey module

Note: CVD risk is the probability of having a heart attack or stroke within the next 10 years. We also ask about the probability of getting diabetes within the next 10 years. Sections B, D & F also ask about perceptions of life expectancy and probability of survival to 80.

Q2: Do elicited beliefs incorporate information about objective risks?

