The primary sampling unit (PSU) and the level at which treatment will be randomly allocated is the barangay. The is the lowest administrative unit in the Philippines. There are 849 barangays in Nueva Ecija. Barangays will be randomly drawn for inclusion in the study and randomly allocated to one of the two treatment groups or the control group with probabilities set to achieve the required sizes of the groups.

Within a barangay, interval sampling will be used: starting from a random location, a procedure will be followed to randomly select households moving out from that point. Selected households will be screened to establish whether each includes anyone aged from 40 to 70 inclusive. If so, one such person will be randomly selected as the main survey respondent and the potential subject of the intervention in the treatment group barangays. Further screening will be undertaken to establish whether the selected person is eligible for the study, mainly on the basis of CVD history (see next section). In addition to the main respondent, we will ask the head of household, spouse or other adult to answer questions about the household in general.

9. Inclusion and exclusion criteria

We restrict attention to individuals aged 40 and above because this is one of the criteria for proceeding from risk assessment to risk screening under the PhilPEN protocol. Hence, we know that all respondents

induced to go for a checkup should be given a full screen with tests for blood glucose, urine protein and, if available, blood lipids. By restricting attention to the 40+ age group, we focus on the population in which CVD risks begin to rise steeply and preventive care is most needed. In addition, Globorisk predicts 10-year CVD risk only for individuals aged 40-74. We exclude those older than 70 because comorbidities are likely to rise steeply beyond that age, and because older individuals are likely to be more cognitively challenged in responding to the risk perceptions and risk attitudes questions.

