10.1 Parameter values

To the extent that it is possible given the estimates available, we have strived to base the choice of parameter values on evidence. However, it must be acknowledged that, as is often the case with power calculations, the evidence is often lacking or meagre, and we often must resort to guesstimates. In doing so, we have endeavoured to err on the side of conservatism and have conducted sensitivity analyses.

Power

Power is set to 80% and statistical significance to 5%.

Minimum detectable effect size

We calculate the sample size necessary to detect a small effect size (δ) defined as 0.2 standard deviation (SD) units (Cohen 1992). Consider our main outcome i) – the 10-year risk of a heart attack or stroke predicted by the office-based Globorisk algorithim. Given an estimated mean 10-year CVD risk of 11.35% in the control group, which we obtain from Globorisk for individuals aged 40-69 with mean values of all risk factors, if the standard deviation is one fifth of the mean, then an effect size of 0.2 SD corresponds to a 4% reduction in the mean. The assumption that the standard deviation is one fifth of the mean is based on estimates of the distribution of 10-year CVD risk scores (Gale et al 2014; Gray et al 2014). However, we caution that these estimates are not obtained using the Globorisk algorithm and most are for samples of high-income country populations.⁷

We deliberately choose a small effect size in order to ensure that our samples will be sufficient to detect only marginal impacts of the interventions on the risk factors that determine the CVD risk prediction. The logic is threefold. First, risk factors such as smoking and weight are notoriously hard to influence. Second, our information intervention is of unknown effectiveness and we recognize a possibility that a non-negligible fraction of respondents are unable to absorb the information provided on their CVD risks. Third, while the procedures defined by the PhilPEN protocol are proven to be effective, our aim is to establish effectiveness as the program is implemented, which may fall well short of the stipulated testing, medication and counselling.

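### The first H2e test pools ages 40 to 70 with no age term, so its slope mixes the age gradient with the association among people of the same age

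*Combined protocol and SAP*

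**What the plan says.** H2e states: "Perceived personal CVD risk is negatively correlated with perceived life expectancies and survival probabilities". The first of its two tests is "Regress perceived personal CVD risk on perceived life expectancies and on survival probabilities until the age of 80 years (section D"). No age term, other covariate or age stratum is named, and the text does not say whether the two regressors enter together.

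The other relevant places are:

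- **Age range** (section 8): "Selected households will be screened to establish whether each includes anyone aged from 40 to 70 inclusive".
- **CVD horizon** (note to Table 1): "CVD risk is the probability of having a heart attack or stroke within the next 10 years". The horizon is fixed at 10 years from the interview.
- **Survival question** (same note): "Sections B, D & F also ask about perceptions of life expectancy and probability of survival to 80". The target age is fixed, so it lies 40 years ahead at age 40 and 10 years ahead at age 70.
- **Age gradient** (section 9): "we focus on the population in which CVD risks begin to rise steeply and preventive care is most needed". No figure is given, and the statement concerns actual rather than perceived risk.
- **Sample** (footnote 3, attached to H2a): the lottery arm is left out because "later tests make use of the information intervention and we want to have a consistent sample throughout".

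Neighbouring tests do allow for such characteristics. H2b regresses on risk factors, H2d repeats its computations by gender and age category, and the H3a regressions carry a covariate vector.

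**The concern.** A reader will take H2e as a check on whether beliefs hang together: someone who thinks a heart attack or stroke more likely should expect to die sooner. That is a statement about people who are otherwise alike, above all in age. Pooling 30 years of age without adjustment brings in a second source of covariation. Older respondents face a higher 10-year CVD risk, yet they have already survived longer and so have a better chance of reaching 80 and a later expected age at death. Their remaining years are fewer.

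Age therefore works against H2e for survival to 80 and for life expectancy given as age at death, and in favour of H2e for life expectancy given as remaining years. At stake is the reading of the test: coherent beliefs could be reported as incoherent, or unlinked beliefs as linked.

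**Working it through.** **No H2e figure to reproduce.** The plan gives no sample size, effect or power for H2e. For N, Table 6 (binary outcomes) gives 299 information + 1,361 control = 1,660 at follow-up, or 1,660/0.9 = 1,844 before 10% attrition. As a check on those inputs:

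- Per arm: 2 × (2.8016/(0.2 × 0.6))² × (1 + 9 × 0.1) × (1 − 0.6²) = 1,326 (Table 6: 1,306–1,361).
- Information arm against 1,361 controls: 1.216/((0.2/2.8016)² − 1.216/1,361) = 289 (Table 6: 287–299).

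**Direction of the age effect.** On a common survival curve S, the chance of reaching 80 from current age a is S(80)/S(a). S(a) falls with a, so the ratio rises, as does expected age at death.

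Example with an assumed Gompertz hazard 0.003·exp(0.08(x − 40)) and an assumed average CVD risk of 4% at 40 and 24% at 70. The second was chosen to sit near the plan's mean: "Given an estimated mean 10-year CVD risk of 11.35% in the control group".

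- Reach 80 from 40: exp(−0.0375 × (24.53 − 1)) = 0.41.
- Reach 80 from 70: exp(−0.0375 × (24.53 − 11.02)) = 0.60.
- Expected age at death: 75.6 at 40 and 82.9 at 70.
- Remaining years: 75.6 − 40 = 35.6 and 82.9 − 70 = 12.9.

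Between these two average, fully coherent people, CVD risk rises by 20 points while survival to 80 rises by 19 points and age at death by 7.3 years. Remaining years fall by 22.7.

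**Simulation A.** N = 1,660, 100 replicates, OLS, two-sided 5% (sidedness is not stated for H2e), clustering ignored. Assumed: uniform age; CVD risk log-linear in age, 4% to 24% (steep) or 7% to 17% (shallow); three Gompertz settings; reporting SDs of 5 points (risk), 5 years (life expectancy) and 15 points (survival). The link is the slope of log mortality on log CVD risk. The adjusted model adds age and age squared. Entries are the share of runs significant in the direction shown, as a range over the mortality settings.

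| Scenario | Survival to 80, no age | Age at death, no age | Remaining years, no age | With age terms |
|---|---|---|---|---|
| Link 0.5, log-SD 0.3, steep | positive 84–100% | positive 100% | negative 100% | negative 100% |
| Link 0.5, log-SD 0.5, steep | negative 93–99% | positive 5–79%, never negative | negative 100% | negative 100% |
| No link, steep | positive 100% | positive 100% | negative 100% | either sign 4–5% |
| No link, shallow | positive 96–100% | positive 100% | negative 100% | either sign 2–7% |

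With link 0.25 and log-SD 0.5, the unadjusted slope was significantly positive in 62% of runs (survival to 80) and 100% (age at death). Across all linked scenarios the adjusted slope was negative in 99–100%. Entering survival to 80 jointly did not remove the false negative slope on remaining years.

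**Simulation B.** N = 1,844, noisier reports (SDs 10 points, 6 years, 15 points), sixfold gradient unless stated.

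- Log-SD 0.4, link 0.5, Gompertz mode 72–82: age at death was significantly positive in 25–100% of runs and never significantly negative. Survival to 80 was significantly negative in only 7–30%. With age dummies, power was 94–100% for both.
- Log-SD 0.8 or 1.0 (mode 77, slope 0.09): correct negative sign without adjustment in 100%, both measures.
- Gradient 2.5-fold, log-SD 0.6 or more (same mortality): correct in 98–100%, both measures.
- Gradient twofold, log-SD 0.4, link 0.5 (same mortality): survival to 80 correct in 100%; age at death correct in 24%, with no wrong signs.

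**The case against.** **H2e is worded as an unconditional correlation, and the regression tests exactly that.** True. The raw correlation can be reported. But its sign cannot then be read as evidence for or against coherent beliefs, because coherent respondents can produce either sign across ages.

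**The wrong sign needs particular conditions.** This stands. The plan gives no age gradient for perceived risk, and H2a and H2b leave open how far perceptions follow objective risk factors. Dot-based answers from respondents with limited numeracy may be widely spread. With a large spread, or a shallower gradient combined with moderate spread, the unadjusted sign is right. For survival to 80 the reversal appeared only at a log-SD of 0.3 or a link of 0.25; elsewhere the effect was attenuation or loss of power.

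**Other tests avoid the problem.** This also stands. The second H2e test compares life expectancy given a CVD event with unconditional life expectancy in the same respondent, and H3b correlates each respondent's own changes in belief (information arm only). Neither is exposed to cross-sectional age in this way. They do not repair the first test, which alone addresses the stated correlation.

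**Two stronger readings are tempting.** One is that the regression tests only the age gradient. That is so only when no link exists at a given age; otherwise the slope is a mixture. The other is that the test would confirm H2e for unlinked beliefs. For coherent age patterns this arises only if life expectancy is recorded as remaining years. The available text does not show that wording, and with age at death or survival to 80 the unlinked case came out positive, against H2e.

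**Conclusion.** The point holds in a limited form. The first H2e slope combines two associations, and age biases it towards positive for survival to 80 and age at death. Under assumed steep gradients and a log-SD of about 0.3–0.4, it can be null or wrong-signed for coherent beliefs; with large person-to-person spread it keeps the right sign. If life expectancy is asked as remaining years, age alone can yield a significant negative slope.

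The direction of the bias is firm provided that respondents reason from a common survival curve and perceived CVD risk rises with age. The percentages are not firm: they depend on assumed mortality, gradient, spread and reporting noise.

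The consequence is modest. H2e is a secondary check on the validity of beliefs. The principal outcome, the treatment-effect estimates and the sample size do not depend on it. The change is still worth making because it is nearly free and can alter the H2e conclusion.

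**What to change.** Add flexible age terms to the H2e regressions, either single-year age dummies or age-by-sex cells. State that the H2e conclusion rests on the within-age slope, and report the unadjusted correlation as descriptive only. State also whether life expectancy is analysed as age at death or as remaining years; once single-year dummies are in the model, the choice no longer matters to the slope when age is in whole years. Fitting life expectancy and survival to 80 in separate regressions is optional, but the plan should say which is done.

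The cost is a line or two of analysis text. Age and sex are already collected. Single-year dummies for ages 40 to 70 use 31 − 1 = 30 degrees of freedom out of 1,660–1,844 respondents.
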